10.2 Sample size determination

60 is the sample size as per the phase (Exploratory trial) of the clinical trial. 30 subjects will be enrolled in each group.

11. Criteria for Success of Treatment

Prevention or non-transformation of IGT to full blown diabetes which is measured by the primary end point will be considered as criteria stated above.

12. Trial Monitoring and Data Analyses

The progress of the trial will be monitored by the Guide. Data analysis will be done by the investigator.

13. Ethical Review

Institutional Ethical Committee (IEC) of participating centre is sought for clearance certificate before the project is initiated. Patient's information sheet and informed consent form will be submitted (Regional Language - Tamil) along with project proposal for approval by IEC. Both will be maintained in duplicate. Consent form will be given to the subject and will be enrolled with proper consent. One copy of Patient Information Sheet (PIS) will be given to the patient at the time of entry to the trial.

Reference:

1. Shukla s.s et al fundamental aspects and basic concepts of Siddha medicines. SYST-Re pharm 2011; 2:48-54.
3. American Diabetes Association. Diagnosis and classification of diabetes mellitus. *Diabetes Care*.2010; 33:S62–S69.
4. Unwin N et al, Impaired glucose tolerance and impaired fasting glycaemia: the current status on definition and intervention. *Diabet Med*. 2002; 19:708–723.
5. International Expert Committee. International Expert Committee report on the role of the A1C assay in the diagnosis of diabetes. *Diabetes Care*. 2009; 32:1327–1334.
6. Anjana RM et al, Prevalence of diabetes and prediabetes (impaired fasting glucose and/or impaired glucose tolerance) in urban and rural India: Phase I results of the Indian Council of medical research-India Diabetes (ICMR-INDIAB) study, 2011, *Diabetologia*, 54:3022-7.
7. Diagnosis, Prognosis, and Treatment of Impaired Glucose Tolerance and Impaired Fasting Glucose, McMaster University Evidence-based Practice Center, Hamilton, Ontario, Canada
<http://archive.ahrq.gov/downloads/pub/evidence/pdf/impglucose/impglucose.pdf>
8. The Diabetes prevention program (DPP) Research Group. *Diabetes care*, 2002, 25:2165-2171.

**OPEN LABELED RANDOMIZED CONTROLLED CLINICAL TRIAL ON
IMPAIRED GLUCOSE TOLERANCE –IGT (Munneerizhivu)**

FORM I - SCREENING PROFORMA

1. Code No (of clinical trial)
2. Centre: _____
3. Name of the Patient _____
4. S. No. of Patient _____
5. Gender Male (1) Female (2)
6. Date of Birth Age (Years)
7. Address _____

Mobile:

Phone no:

CRITERIA FOR INCLUSION

Yes (1)

No (0)

- | | | |
|---|----------------------|----------------------|
| 8. Age between 30 years and 60 years |  |  |
| 9. OGTT – After 2 hours < 140 mg and > 199 mg |  |  |
| 10. Glycated hemoglobin (HBA1C) >6.0% and <6.5% |  |  |

11. Blood sugar – Fasting > 100 and =< 125 mg/dl

CRITERIA FOR EXCLUSION

12. Age below 30 and above 60 years.

13. Malignant and accelerated hypertensive

14. CVS disorder (CAD)

15. Pregnant woman or the women planning to be pregnant in next six months

16. Lactating mothers

17. Secondary Diabetes mellitus

18. Patient undergoing regular treatment for Diabetes or for any other severe illness

19. CNS disorder e.g. encephalopathy

If yes to S.No.8-11 admit the patient into the study.

If admitted subject _____ No. _____

Date: _____

Signature of the Doctor _____

**OPEN LABELED RANDOMIZED CONTROLLED CLINICAL TRIAL ON
IMPAIRED GLUCOSE TOLERANCE –IGT (Munneerizhivu)**

FORM I A – SELECTION PROFORMA

1. Code No. (Clinical trial)
2. Centre :
3. Name of the Patient _____
4. S. No. of Patient _____
5. Gender Male (1) Female (2)
6. Date of Birth Age (Years)
7. Address _____

8. Educational status
Illiterate (1) Read & Write (2)
Educational qualifications _____ (3)
9. Occupation
Desk Work (1) Field Work (2) Others Specify _____
10. Income per capita per month in ₹ _____

Chief complaint with duration (if any) in days (mostly asymptomatic)

- | | Absent (0) | Present (1) |
|------------------------------------|----------------------|----------------------|
| 11. Polyuria (Excessive Urine) |  |  |
| If present, duration in days _____ | | |
| 12. Polyphagia (Excessive Hunger) |  |  |
| If present, duration in days _____ | | |
| 13. Polydipsia(Excessive Thirst) |  |  |
| If present, duration in days _____ | | |

Absent (0)

Present (1)

14. Exhaustion/Tiredness

If present, duration in days _____

15. Body ache

If present, duration in days _____

Personal History:

16. Diet Veg (1) Non-veg (2) Lacto-veg (3)

17. Presence of anxiety No Yes

18. Constipation No Yes

19. Physical activity less active

Addiction

20. Smoking No (0) Yes (1)

If yes, specify:

(a) Quantity [packs] _____ (b) Total duration in years _____

21. Tobacco No Yes

If yes, specify: (a) quantity _____ b) Total duration in years _____

22. Alcohol No (0) Yes (1)

23. If yes, specify: quantity(ml) _____

24. Total duration in years _____

25. Any other (specify) _____

26. Yakkaiyin Ilakkanam (Type of body constitution)

VITAL SIGNS

27. Pulse rate/min

28. Heart rate/min

29. BP(mm of Hg)

 /

30. Temperature °F

 °

31. Cyanosis

PRESENT(1)

ABSENT (2)

32. Anaemia

33. Jaundice

34. Clubbing

35. Lymphadenopathy

36. Oedema

37. Height/cm

 cm

38. Weight/Kgs

 Kgs

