The investigational drug is a polyherbal Siddha formulation. It is proven as an anti-diabetic^{3, 4, 6}. Some studies have investigated the possible anti-diabetic properties of combination drug in animal models, one in a high fructose diet induced and another in alloxan diabetic rats^{3, 5}. The results of these studies show that the administration of the extracts reduced the blood sugar level. Gallic acid is the component present in the composition of investigational drug having anti-diabetic activity⁷. More over the same studies highlighted the anti-oxidant and anti-obesity effects of this drug. These effects are assumed to play a major role to reduce the chances of transition of IGT patients to established diabetics. According to ICMR-INDIAB study conducted

in 2011, 3.9 million are estimated to be in the state of prediabetes in Tamil Nadu. Projections for the whole of India would be 77.2 million pre-diabetic patients¹⁰. So a poly-herbal formulation which is more effective, cost effective and safety among prediabetes patients.

According to the above references life style modification is done holistically in this study with the study drug.

2. Clinical Study Objectives:

2.1 Primary objective:

To assess the efficacy of Siddha formulation in the individuals having Impaired Glucose Tolerance (IGT) – (Munneerizhivu). If, during treatment or after treatment OGTT 2 hours remain between 126 mg/dl and 140 mg/dl, fasting blood sugar between 70 mg/dl and 100 mg/dl and HbA1c is $\leq 6.0\%$ it will be treated as successful outcome of the treatment.

2.2 Secondary objective:

To determine the Toxicological data of Siddha formulation

[figure not shown]
3 Study Design:

Open labelled Randomized Controlled Clinical Trial.

There will be two arms in this study. To one group is assigned life style modification and test drug and to the other group Life Style Modification (LSM). Randomization will be achieved through Random numbers.

3.1 Allocation to treatment:

The subjects will be allocated to the drug interventional group and LSM group based on the Random numbers generated by the computer.

Schematic representation of Study Design

5 Criteria for Inclusion:

Subjects in their 3rd to 6th decade only will be included in this study. Subjects falling in any one of the following criteria i.e. 2 hours OGTT should be between 140 mg and 199 mg. Glycated hemoglobin (HbA1C) > 6.0% and <6.5% and Blood sugar – Fasting > 100 and =< 125 mg/dl will be included.

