6.1.1 Withdrawal of subjects due to non-compliance/ adherence

The investigator shall withdraw the patients from both groups of the study if

- Fasting blood sugar rises > 126 mg. /dl, or 2 hours OGTT blood sugar level increases > 199 mg/dl and are not controllable within 90 days.
- Any serious complication develops which requires urgent treatment with any other drug / therapy.

The investigator will mention the probable cause of withdrawal and provide possible medical treatment to manage the illness. The patient will be withdrawn if the above said parameters shoot up in his blood picture due to non-compliance.

6.2 Study Drug Supplies:

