7.2 Follow-up Procedure

A prospective observation will be done for a period of one month after completion of the trial (6 months) by both groups. The drug intervention will be withdrawn in the drug group and LSM group will be on normal life style to measure the efficacy of the trial drug and LSM in both the groups. A comparison (physical assessment and blood sugar (OGTT) between the trial and non-trial period will be drawn in the outcome.

8. Safety and Efficacy Assessments

Liver function test and renal function test are recorded before and after trial drug administration to measure the safety of the drug. OGTT, HbA1c and blood glucose levels also measured for efficacy of the drug. Lipid profile is tested to measure the complementary benefit of the drug in microvascular end arterial diseases.

9. Adverse Event Reporting

If any adverse drug reaction or adverse event is reported, the study subject will be referred to the Pharmacovigilance cell of the study centre. According to the advice of the Pharmacovigilance cell withdrawal or continuation of the study will be determined.

10. Statistical Methods/Data Analysis

All the data will be entered in the Microsoft excel and the data will be analyzed using SPSS Version 16. Quantitative data shall be given in mean and standard deviation. Prevalence

shall be given in proportion with 95% confidence interval. Association with risk factors shall be analyzed using chi square test and multivariate analysis. Correlation shall be analyzed using Karl Pearson, with significant level ($P < 0.005$ or $P < 0.05$). Comparison between means with Annovatest, difference between means assessed by paired t test. Further analysis will be extended depending upon the results at the end of the study.

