10.1 Study endpoints

10.1.1 Primary endpoint

During treatment or after treatment OGTT 2 hours result is < 140 mg/dl, fasting blood sugar is < 100 mg/dl and HbA1c is < 6.0 % it will be treated as successful outcome of the treatment.

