10.1.2 Secondary endpoints

Normal Liver function test and renal function test should be taken as success end point towards safety.

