41. SGOT (IU/L) _____

- 42. SGPT (IU/L) _____
- 43. Alk. Phosphatase (KA units) _____
- 44. Total proteins (gm/dl) _____
- 45. Albumin (gm/dl) _____
- 46. Globulin (gm/dl) _____
- 47. A/G Ratio _____

Serum Electrolytes

- 48. Sodium (mEq/L) _____
- 49. Potassium (mEq/L) _____
- 50. Chloride (mEq/L) _____

Sl.No.10-50 will be done during I visit (0 day), IV visit (90th day) and VII visit (180th day).

Sl.No.28 & 29 (Blood Sugar- F & PP) in the following visits II, III, V and VI.

Date:

--	--

--	--

--	--

Signature of Investigator/ Medical Officer

**OPEN LABELED RANDOMIZED CONTROLLED CLINICAL TRIAL ON
IMPAIRED GLUCOSE TOLERANCE –IGT (Munneerizhivu)**

**FORM II - CLINICAL & PHYSIOLOGICAL ASSESSMENT
[Before Treatment & During monthly visit]**

1 st visit – 0 day		5 th visit – 120 th day	
2 nd visit – 30 th day		6 th visit – 150 th day	
3 rd visit – 60 th day		7 th visit – 180 th day	
4 th visit – 90 th day		8 th visit – 210 th day	

1. Code No. (Clinical trial)
2. Centre : Siddha Central Research Institute, Arumbakkam, Chennai.
3. Name of the Patient _____
4. S. No. of Patient _____
5. Gender Male (1) Female (2)
6. Date of Birth Age (Years)
7. Address _____

Chief complaint with duration (if any) in days (mostly asymptomatic)

- | | Absent (0) | Present (1) |
|------------------------------------|---|---|
| 8. Polyuria (Excessive Urine) |  |  |
| If present, duration in days _____ | | |
| 9. Polyphagia (Excessive Hunger) |  |  |
| If present, duration in days _____ | | |
| 10. Polydipsia(Excessive Thirst) |  |  |

If present, duration in days _____

11. Exhaustion/Tiredness

If present, duration in days _____

Absent (0)

Present (1)

12. Body ache

If present, duration in days _____

VITAL SIGNS

13. Pulse rate/min

14. Heart rate/min

15. BP(mm of Hg)

 /

16. Temperature °F

 .

PRESENT(1)

ABSENT (2)

17. Cyanosis

18. Anaemia

19. Jaundice

20. Clubbing

21. Lymphadenopathy

22. Oedema

23. Height/cm

 .

24. Weight/Kgs

 .

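### Section 11 says the primary endpoint measures non-transformation to diabetes, but 10.1.1 scores only normalisation and no named endpoint counts progression

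*Protocol*

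**What the plan says.** - **Section 11 (criteria for success):** success is "Prevention or non-transformation of IGT to full blown diabetes which is measured by the primary end point". The sentence then refers back to the criteria given earlier.
- **Section 10.1.1 (primary endpoint):** success, at any point during or after treatment, is that "OGTT 2 hours result is < 140 mg/dl, fasting blood sugar is < 100 mg/dl and HbA1c is < 6.0" per cent. Section 2.1 also defines success by near-normal ranges on the same three tests, with no diabetes threshold.
- **Section 10.1.2 (the only secondary endpoint):** "Normal Liver function test and renal function test should be taken as success end point towards safety".
- **Section 6.1.1 (withdrawal, both groups):** diabetes-range limits appear here, as fasting above 126 mg/dl or 2-hour OGTT above 199 mg/dl, for values that "are not controllable within 90 days". The investigator notes the probable cause and provides treatment.
- **Section 1.1 (rationale):** the drug's effects are expected to "reduce the chances of transition of IGT patients to established diabetics".
- **Form III, footer:** the full laboratory panel, including fasting sugar, OGTT and HbA1c, is scheduled at days 0, 90 and 180. For the months between: "Sl.No.28 & 29 (Blood Sugar- F & PP) in the following visits II, III, V and VI".

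**The concern.** The rationale is fewer transitions to diabetes, and Section 11 turns that into the success criterion and names the endpoint said to measure it. If that endpoint measures something else, a favourable result would be reported as prevention of diabetes without anyone having counted who became diabetic. The error can run either way. A gain in normalisation may come with no difference in progression, and a difference in progression may sit behind equal normalisation rates.

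**Working it through.** The plan has no figure to reproduce here. The sample size of 60 is justified only by the exploratory phase, with no event rate, effect or power. The main check is to classify the same participant under both sections.

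**Step 1. Classification**

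| Participant | Section 11 (not transformed) | Section 10.1.1 (normalised) |
|---|---|---|
| Below all three limits throughout | success | success |
| Stays at OGTT 160, fasting 110, HbA1c 6.2% | success | not a success |
| In the diabetes range, never normalised | failure | not a success |
| Below all three limits at day 90, OGTT above 199 at day 180 | failure | can be a success |

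Rows 2 and 3 share one class under 10.1.1, although Section 11 exists to tell them apart. Row 4 follows from allowing success at any time, together with the Form III footer, which puts all three tests at day 90. The note beside the HbA1c item on that form mentions only the start and end of treatment, so row 4 depends on the footer being followed. Rows 2 and 3 do not.

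**Step 2. Whether the difference could matter numerically**

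The only input from the protocol is n = 30 per arm (Section 10.2). All counts and rates below are assumed, and within each example nobody both normalises and later progresses.

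- *Example A:* 20% versus 40% normalised, 10% progressed in both arms. Under 10.1.1: 30 × 0.20 = 6 versus 30 × 0.40 = 12 successes. Under Section 11: 30 × 0.90 = 27 versus 27. The primary endpoint shows a gain and progression shows none.
- *Example B:* 3/30 normalised in each arm, 2/30 versus 9/30 progressed. Under 10.1.1: 3/30 − 3/30 = 0. Progression: 9/30 − 2/30 = 7/30 = 23.3 points (Newcombe 95% CI 3.5 to 41.8). The primary endpoint shows nothing.

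**Step 3. Precision of a progression count**

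The exact (Clopper-Pearson) 95% limits for x of n are the 2.5% quantile of Beta(x, n − x + 1) and the 97.5% quantile of Beta(x + 1, n − x). With n = 30:

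- 2/30 = 6.7%, CI 0.8% to 22.1%
- 9/30 = 30.0%, CI 14.7% to 49.4%

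Power to detect a halving of risk (normal approximation for two proportions, two-sided alpha 0.05, 30 per arm):

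| Assumed control risk | Expected control events | Power |
|---|---|---|
| 5% | 1.5 | 7% |
| 10% | 3 | 11% |
| 20% | 6 | 19% |

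A progression count can therefore describe, but not test.

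**The case against.** The best defence is that there is only one operative rule. Section 11 sets no rival threshold and points back to 10.1.1, so nobody would be scored differently because of it. A participant normal on all three tests has not transformed at that assessment, which makes normalisation a stricter form of the same idea. This stands as far as scoring goes. It does not rescue the statement that the endpoint measures non-transformation, because the reference back leads only to the normalisation limits.

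Three stronger readings are tempting, and the documents do not support them.

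- *Progression goes unrecorded.* It does not. Blood sugar is scheduled at every visit to day 180, and Section 6.1.1 applies to both groups with the cause noted. Section 10 plans proportions with confidence intervals and leaves room for further analysis. Its planned "Comparison between means with Annovatest, difference between means assessed by paired t test" may reflect part of a difference. What is missing is a named endpoint that counts who progressed.
- *Every participant who progresses is scored a non-success.* The wording on timing prevents this (row 4 of the table), so the normalisation count does not even cap the number who progressed.
- *The withdrawal rule must miss late rises because its 90 days run out after day 180.* The protocol does not say when the 90 days start, and Section 7.2 plans an OGTT at the follow-up one month later, at the day-210 visit.

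How withdrawn participants enter the analysis is partly a matter for a statistical analysis plan, which is not at hand, so its absence here is not held against the protocol. Such a plan could add a table but could not make Section 11 correct.

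**Conclusion.** The point holds as a false statement about what the primary endpoint measures. Section 10.1.1 measures normalisation of glycaemia, and a result on it cannot support a conclusion about non-transformation to diabetes. This rests on comparing definitions and needs no assumption about rates. The day-90 route to success additionally assumes that HbA1c is taken at day 90 as the Form III footer provides. The effect in this trial cannot be quantified from the documents, and the 0 versus 23-point contrast only illustrates how far the two definitions can part. The trial can run as designed, but the correction should be made before results are read.

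**What to change.** 1. Reword Section 11 to say that the primary endpoint measures normalisation of glycaemia and does not measure progression to diabetes. This alone removes the false statement.
2. Add to Section 10.1 a descriptive secondary endpoint: progression to diabetes-range values by day 180, from tests already scheduled.
   - *Cut-offs:* 2-hour OGTT above 199 mg/dl, HbA1c 6.5% or more, and one fasting limit used both here and in Section 6.1.1. At present entry stops at 125 mg/dl and withdrawal starts above 126.
   - *Baseline condition:* count a test only for participants below its diabetes threshold at entry. Section 5 lists "Glycated hemoglobin (HbA1C) > 6.0% and <6.5% and Blood sugar – Fasting > 100 and =< 125 mg/dl" and the OGTT range, but asks for any one of its criteria. On that reading someone could enter already in the diabetes range on another test. Form I requires all of them.
   - *Withdrawals:* count those under the glycaemic bullet of Section 6.1.1 as progressed.
   - *Reporting:* number by arm in all randomised participants, with an exact 95% CI and no formal test.

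The cost is protocol wording and one extra table, with no new test or visit. The drawback is the imprecision shown above, which is why the endpoint should be labelled descriptive.

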39. BMI

Date:

Signature of Investigator/ Medical Officer

**OPEN LABELED RANDOMIZED CONTROLLED CLINICAL TRIAL ON
IMPAIRED GLUCOSE TOLERANCE –IGT (Munneerizhivu)**

FORM III - LABORATORY INVESTIGATIONS (Before Treatment – 0 day)

1. Code No. (of clinical trial)
1. Centre: Siddha central Research Institute, Arumbakkam, Chennai.
3. S. No. of Patient _____
4. Name of the Patient _____
5. Address _____

6. Gender Male (1) Female (2)
7. Date of Birth 8. Age (Years)
9. Date of Assessment

**Urine Examination
Routine**

10. Sugar _____ 11.a) Albumin _____ b) Microalbumin _____
12. Deposits _____

Microscopic

13. Pus cell _____ (HPF)
14. RBC _____ (HPF)
15. Cast _____ (HPF)

Stool examination

16. Routine _____

Microscopic

17. Ova _____ 18. Cyst _____ 19. Occult Blood _____

Blood

20. TC (Cells/Cumm) _____

Differential Count

21. P (%) _____ 22. L (%) _____ 23. E (%) _____ 24. M (%) _____ 25. B (%) _____

26. Hb (g/dl) _____.

27. ESR (1/2 hour.) _____ ESR (1 hour.) _____

28. Blood Sugar- Fasting (mg/dl) _____

29. Blood Sugar – OGTT (mg/dl) _____ (After 2 hours)/ PP _____ (mg/dl)

30. Glycated Hemoglobin (HbA1c) _____ (to be done before treatment and at the end of treatment)

31. Blood Urea (mg/dl) _____

32. S. Creatinine (mg/dl) _____

33. Uric acid (mg/dl) _____

LIPID PROFILE

34. Serum total Cholesterol (mg/dl) _____

35. S. Triglycerides (mg/dl) _____

36. HDL (mg/dl) _____

37. LDL (mg/dl) _____

38. VLDL (mg/dl) _____

LIVER FUNCTION TEST

Serum Bilirubin

39. Total (mg/dl) _____

40. Direct (mg/dl) _____

41. SGOT (IU/L) _____

- 42. SGPT (IU/L) _____
- 43. Alk. Phosphatase (KA units) _____
- 44. Total proteins (gm/dl) _____
- 45. Albumin (gm/dl) _____
- 46. Globulin (gm/dl) _____
- 47. A/G Ratio _____

Serum Electrolytes

- 48. Sodium (mEq/L) _____
- 49. Potassium (mEq/L) _____
- 50. Chloride (mEq/L) _____

Sl.No.10-50 will be done during I visit (0 day), IV visit (90th day) and VII visit (180th day).

Sl.No.28 & 29 (Blood Sugar- F & PP) in the following visits II, III, V and VI.

Date:

--	--

--	--

--	--

Signature of Investigator/ Medical Officer

**OPEN LABELED RANDOMIZED CONTROLLED CLINICAL TRIAL ON
IMPAIRED GLUCOSE TOLERANCE –IGT (Munneerizhivu)**

**FORM II - CLINICAL & PHYSIOLOGICAL ASSESSMENT
[Before Treatment & During monthly visit]**

1 st visit – 0 day		5 th visit – 120 th day	
2 nd visit – 30 th day		6 th visit – 150 th day	
3 rd visit – 60 th day		7 th visit – 180 th day	
4 th visit – 90 th day		8 th visit – 210 th day	

1. Code No. (Clinical trial)
2. Centre : Siddha Central Research Institute, Arumbakkam, Chennai.
3. Name of the Patient _____
4. S. No. of Patient _____
5. Gender Male (1) Female (2)
6. Date of Birth Age (Years)
7. Address _____

Chief complaint with duration (if any) in days (mostly asymptomatic)

- | | Absent (0) | Present (1) |
|------------------------------------|---|---|
| 8. Polyuria (Excessive Urine) |  |  |
| If present, duration in days _____ | | |
| 9. Polyphagia (Excessive Hunger) |  |  |
| If present, duration in days _____ | | |
| 10. Polydipsia(Excessive Thirst) |  |  |

If present, duration in days _____

11. Exhaustion/Tiredness

If present, duration in days _____

Absent (0)

Present (1)

12. Body ache

If present, duration in days _____

VITAL SIGNS

13. Pulse rate/min

14. Heart rate/min

15. BP(mm of Hg)

 /

16. Temperature °F

 .

PRESENT(1)

ABSENT (2)

17. Cyanosis

18. Anaemia

19. Jaundice

20. Clubbing

21. Lymphadenopathy

22. Oedema

23. Height/cm

 .

24. Weight/Kgs

 .

